5.10 Patient Reported Outcomes (PROs)

^{**}NB32 (Naltrexone SR 32 mg/day and Buproprion SR 360mg/day)

^{***} From week 28-44, nonresponders on NB32 were re-randomized to either continue NB32 or change to Naltrexone SR 48mg/day and Buproprion SR 360mg/day

Being overweight or obese has an important impact on patients' functioning and well-being, particularly physical function⁹⁹. Thus, it will be important to assess the impact of weight loss and POWER-remote on patient-reported outcomes, including pain, fatigue, mental well-being, physical function, endocrine symptoms, sleep, sexual function, and medication adherence. The original POWER study investigated PROs using the MOS SF-12 physical component summary and mental component summary, the EuroQoL-5 dimensions single index and visual analog scale, the Patient Health Questionnaire-8 (PHQ-8) depression symptoms, and the Pittsburgh Sleep Quality Index (PSQI) sleep quality scores at baseline and 6, 12 and 24 months. We will notify the primary oncology provider if the PHQ-8 score is ≥15 (moderately severe or severe depression).

Physical domains were most affected, especially in subjects who lost weight. In another study which involved postmenopausal women undergoing a dietary and/or exercise intervention, weight loss predicted improvement in self-reported physical function, vitality, and mental health ¹⁰⁰. Since physical function has most consistently been found to be improved by weight loss, it will be our primary PRO. Studies in cancer patients suggest a 4-6 point change in score in Physical Function using the National Institute of Health (NIH) Patient-Reported Outcome Measurement Information System (PROMIS) questionnaire to be clinically meaningful ¹⁰¹. Since minimally important differences is usually estimated by taking half the estimated standard deviation, and in conjunction with the aforementioned studies, we conservatively hypothesize that, compared to baseline, weight loss at 6 months will be associated with an increase of five points in PROMIS, as determined by version 1 short-form to assess physical function. This form was also used in the POWER-remote study.

We will also administer a questionnaire to evaluate modulation in other PROs including: pain, fatigue, mental well-being, sleep, endocrine symptoms, and sexual function. Participants will also complete a drug diary to monitor medication adherence.

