7.5.2 Patient Reported Outcomes

We will collect PROs using REDCap, which is already in throughout the institution by several clinical investigations. PROs will include questionnaires regarding physical function, pain, fatigue, mental well-being, endocrine symptoms, sleep, sexual function, and medication adherence, at baseline, 2, and 6 months following initiation of the intervention. Pain, fatigue, mental well-being, sleep, and physical function will be assessed using the NIH PROMIS questionnaire; endocrine symptoms with the FACT-endocrine symptoms, and sexual function

with the MOS-Sexual Function. Medication adherence will be monitored with the institutional drug diary.

Enrolled patients will be given a letter with a username and password for the Fitbit website, and will be oriented on how to use the website; an email address will also be recorded for each participant. Participants will receive e-mail reminders when it is time for them to complete the REDCap questionnaire. They will be encouraged to complete the questionnaire prior to any planned clinic visit; however, they will be informed that a research coordinator can assist them prior to their visit if they prefer to complete the questionnaire at the clinic. Whether patients complete the PRO questionnaire at home or in the clinic, they will access the questionnaires via the internet. At follow-up clinic visits for patients who completed the PRO questionnaires, clinician sub-investigators will have a summary report available to them via REDCap.

Questionnaires will focus on some basic background information and patient reported outcomes, with more detailed survey information as follows. Data from the questionnaires will be available for export into spreadsheets or other tools for analysis.

NOTE: In the event that questionnaires through REDCap are not available, we will use paper-based questionnaires.

The questions that will be included in the REDCap system are included in Appendix E. Score interpretation is in Appendix F. Domains that will be included in REDCap are as follows:

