the impact of fatigue on physical, mental, and social activities. The short form used has 7 questions which assess fatigue over the past seven days. As with all of the PROMIS short forms, each question has five response options ranging in value from one to five. A total raw score is calculated by summing the values of the response to each question, and then translated into a T-score using a conversion table. The T-score rescales the raw score into a standardized score with a mean of 50 and a standard deviation (SD) of 10. Therefore, a person who has a T-score of 40 is one SD below the U.S. general population mean. Reliability and validity of the fatigue assessment in cancer patients has been reported 104.

- Mental health will be evaluated using the NIH PROMIS Depression and Anxiety questionnaires. The Adult Depression Version 1.0 Short Form is an 8 question survey, and the Adult Anxiety Version 1.0 Short Form is a 7-item survey, for a total of 15 mental health questions. The depression item bank assesses self-reported negative mood (sadness, guilt), views of self-criticism, worthlessness), and social cognition (loneliness, interpersonal alienation), as well as decreased positive affect and engagement (loss of interest, meaning, and purpose). The anxiety item bank measures self-reported fear (fearfulness, panic), anxious misery (worry, dread), hyperarousal (tension, nervousness, restlessness), and somatic symptoms related to arousal (racing heart, dizziness). The anxiety and depression scores are calculated individually, in the same way all PROMIS scores are calculated as above.
- Endocrine symptoms will be assessed using the endocrine subscale of the Functional Assessment of Cancer Therapy-Endocrine Symptom questionnaire. The Endocrine Subscale was designed for use with the FACT-B (Functional Assessment of Cancer Therapy for breast cancer patients) but has been tested on its own¹⁰⁵. It comprises 18 items in which patients indicate how true a statement has been for them over the prior 7 days using a 5-point scale.

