7.6 BWL intervention

All patients enrolled will receive a 6 month remotely delivered behavioral lifestyle intervention primarily through a web-based platform. For purposes of this study, lifestyle coaches will be supplied by Johns Hopkins. The coaches are trained in both behavioral weight loss principles and motivational interviewing will have access to self-monitoring data through the platform, allowing them to review multiple aspects of adherence to dietary and physical activity behaviors as well as weight loss progress. To tailor the intervention to breast cancer survivors, we have provided the coaches with comprehensive training regarding breast cancer subtypes, types of therapy patients have received and might still be taking (e.g., hormonal, anti-HER2 agents), expected side effects from prior or ongoing therapy (e.g., fatigue, neuropathy, lymphedema, hot flashes), scheduled standard clinic visits and tests, and symptoms disconcerting for a recurrence. Coaches will discuss additional dietary and physical activity recommendations that are standard for breast cancer patients such as moderation of alcohol intake. Patients are provided with modules of recommended exercises per American College of Sports Medicine and American Cancer Society recommendations, particularly in reference to lymphedema prevention¹¹¹.

The participants will have access to a web-based platform which provides support for lifestyle counseling in behavioral methods of weight management; a summary of the support and methods will be given at the first/in-person visit with the weight loss coach. Participants in this group will be encouraged to record diet, exercise, and weight on this web-based platform. Web-links to health related websites may also be left by the coach. These participants will receive usual medical care from their providers (i.e., oncologists and primary care physicians). Providers will support and encourage participants to be actively engaged in the lifestyle counseling intervention.

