	a. Not at all	ting in strenuous sports	?	
	b. Very littl			
	c. Somewha			
	d. Quite a lo			
	e. Cannot d	0		
2.	Does your health	ı now limit you in walki	ng more than a mile?	
۷.	a. Not at all	•	ing more than a nine:	
	b. Very littl			
	c. Somewha			
	d. Quite a lo	ot		
	e. Cannot d	0		
3.	Does your health	now limit you in climb	oing one flight of stairs	?
	a. Not at all	 	88	
	b. Very littl	e		
	c. Somewha	at		
	d. Quite a lo	ot		
	e. Cannot d	o		
4.	Does your health	ı now limit you in lifting	g or carrying groceries?)
••	a. Not at all	•	J 	
	b. Very littl			
	c. Somewha			
	d Onite a la	nt .		

- e. Cannot do
- 5. Does your health now limit you in bending, kneeling or stooping?
 - a. Not at all
 - b. Very little
 - c. Somewhat
 - d. Quite a lot
 - e. Cannot do
- 6. Are you able to do chores such as vacuuming or yard work?
 - a. Without any difficulty
 - b. With a little difficulty
 - c. With some difficulty
 - d. With much difficulty
 - e. Unable to do
- 7. Are you able to dress yourself, including tying shoelaces and doing buttons?
 - a. Without any difficulty
 - b. With a little difficulty
 - c. With some difficulty
 - d. With much difficulty
 - e. Unable to do
- 8. Are you able to shampoo your hair?
 - a. Without any difficulty
 - b. With a little difficulty
 - c. With some difficulty
 - d. With much difficulty
 - e. Unable to do
- 9. Are you able to wash and dry your body?
 - a. Without any difficulty
 - b. With a little difficulty
 - c. With some difficulty
 - d. With much difficulty
 - e. Unable to do
- 10. Are you able to get on and off the toilet?
 - a. Without any difficulty
 - b. With a little difficulty
 - c. With some difficulty
 - d. With much difficulty
 - e. Unable to do

VI. Patient Reported Outcomes (PROs) - Anxiety

In the past 7 days......

- 1. I felt fearful
 - a. Never
 - b. Rarely
 - c. Sometimes
 - d. Often
 - e. Always
- 2. I felt anxious
 - a. Never
 - b. Rarely
 - c. Sometimes
 - d. Often
 - e. Always
- 3. I felt worried
 - a. Never
 - b. Rarely
 - c. Sometimes
 - d. Often
 - e. Always
- 4. I found it hard to focus on anything other than my anxiety
 - a. Never
 - b. Rarely
 - c. Sometimes
 - d. Often
 - e. Always
- 5. I felt nervous
 - a. Never
 - b. Rarely
 - c. Sometimes
 - d. Often
 - e. Always
- 6. I felt uneasy
 - a. Never
 - b. Rarely
 - c. Sometimes
 - d. Often
 - e. Always

- 7. I felt tense
 - a. Never
 - b. Rarely
 - c. Sometimes
 - d. Often
 - e. Always

VII. Patient Reported Outcomes (PROs) - Depression

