APPENDIX F: Score Interpretation

NOTE: Please see below an example of the information to be provided to the participant upon completion of the questionnaires. This information will be also available to the providers to discuss with participants during their clinic visit.

The reports produced by the system will highlight scores that are potential 'problems' because they represent either particularly poor health, quality of life below average, or significant worsening from the last time point, as follows:

Sleep Disturbance, Physical Function, Anxiety, Depression, Pain Impact, and Fatigue:

- Higher scores represent more of what is being measured (e.g., higher scores indicate better physical function and worse fatigue).
- A score of 30-70 is considered within the expected range of an average population of patients.
- Highlighted scores are either outside of that range (less than 30 for physical function; greater than 70 for all others) or are a significant change from previous answers.

Sexual Function:

- Higher scores indicate more problems with sexual function.
- A score of less than 40 is considered to be within the expected range of an average population of patients.
- Highlighted scores are above that average range (greater than 40) or a significant increase from previous answers.

Endocrine Symptoms:

- Higher scores indicate better quality of life.
- A score of 41.3 76 is considered to be within the expected range for an average population of women.
- Highlighted scores are below that average range (less than 41.3) or a significant decrease from previous answers.

Godin Leisure-Time Exercise questionnaire

- For the first question, weekly frequencies of strenuous, moderate, and light activities are multiplied by nine, five, and three, respectively.
- Total weekly leisure activity is calculated in arbitrary units by summing the products of the separate components, as shown in the following formula: Weekly leisure activity score = $(9 \times \text{Strenuous}) + (5 \times \text{Moderate}) + (3 \times \text{Light})$.
- For example: Strenuous = 3 times/wk. Moderate = 6 times/wk, and Light = 14 times/wk. Then, the total leisure activity score = $(9 \times 3) + (5 \times 6) + (3 \times 14) = 27 + 30 + 42 = 99$.
- Godin scale score of ≥24 is active, 14-23 is moderately active, and <14 is insufficient active or sedentary.

Statistical Considerations

Sleep Disturbance, Physical Function, Anxiety, Depression, Pain Impact, and Fatigue:

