- Surveys were validated in the general population.
- All of these domains are mapped to a mean score of 50, with a standard deviation of 10.
- Highlighted scores represent a score more than 2 standard deviations from the mean (20 points) or a worsening of at least half a standard deviation (5 points).

Sexual Function:

- This survey was validated in patients with major medical problems with and without depression, and patients without medical problems but with depression.
- For this population, the mean sexual problem scores ranged from 24.48 43.5, with a standard deviation of 32.
- Highlighted scores represent a score that is worse than the average scores among an ill population (40 points) or a worsening of at least half a standard deviation (16 points).

Endocrine Symptoms:

- This survey was validated in female breast cancer patients undergoing a variety of hormone therapies as well as normal controls.
- This survey is mapped to a mean score of 59.7, which is the total group mean from the validated population, with a standard deviation of 9.2.
- Highlighted scores represent a score that is two standard deviations away from the mean (41.3 points) or a worsening of at least half a standard deviation (4.6 points).

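### Section 5.10 promises to notify the oncology provider at PHQ-8 ≥15, but the PHQ-8 is not administered, so the rule cannot operate as written (minor)

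*Combined protocol and SAP*

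**What the plan says.** Section 5.10 first lists the instruments of the original POWER study, the PHQ-8 among them. It then states, in the first person and future tense: "We will notify the primary oncology provider if the PHQ-8 score is ≥15 (moderately severe or severe depression".

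Section 7.5.2, which sets out what this trial collects at baseline, 2 months and 6 months, names another instrument: "Mental health will be evaluated using the NIH PROMIS Depression and Anxiety questionnaires". It describes the depression form as having 8 questions. It also says that the questions to be asked are those in Appendix E, where the only depression block is "VII. Patient Reported Outcomes (PROs) - Depression": eight items on the past 7 days, answered from never to always.

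On what happens to the scores:

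- Section 7.5.2 says that at follow-up clinic visits "clinician sub-investigators will have a summary report available to them via REDCap".
- Appendix F describes "information to be provided to the participant upon completion of the questionnaires" and adds: "This information will be also available to the providers to discuss with participants during their clinic visit".
- For the PROMIS domains Appendix F states: "Highlighted scores represent a score more than 2 standard deviations from the mean (20 points". A worsening of at least 5 points is highlighted as well.

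**The concern.** A numerical trigger with a named recipient reads as an undertaking to participants, and a site or ethics board would take it as one. If the score it depends on is never collected, the undertaking cannot be met. A woman with moderately severe or severe depressive symptoms could complete every questionnaire in the trial without triggering the notification the protocol promises. The form that is given has a report highlight, but no one is required to pass a high score to her oncology provider.

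Entry criteria narrow the affected group without emptying it. Exclusion 6.2.5 removes unstable psychiatric disorder. It does not remove stable or unrecognised depression, and 6.2.7 allows SSRIs and SNRIs at stable doses.

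**Working it through.** The plan has no design figure to reproduce here. The check is to set the sections side by side, followed by two small calculations.

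**Is the PHQ-8 administered?**

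| Place | Depression instrument |
|---|---|
| 5.10 | PHQ-8, once as a POWER study instrument and once in the notification rule |
| 7.5.2 | PROMIS Depression, 8 items |
| Section 8 calendar | None named; generic questionnaire and PRO rows only |
| Appendix E, part VII | Eight items matching the PROMIS form described in 7.5.2 |
| Appendix F | PROMIS highlight rules only |

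The PHQ-8 is absent from the two places that define what participants are asked, 7.5.2 and Appendix E.

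**Can the cut-off of 15 be applied to the PROMIS form?** Under 7.5.2 each item scores 1 to 5 and the sum is converted to a T-score with mean 50 and SD 10.

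- Raw range: 8 × 1 = 8 to 8 × 5 = 40. A raw score of 15 is 15 / 8 = 1.875 per item, where 1 is the lowest response.
- As a T-score, 15 is (15 − 50) / 10 = −3.5 SD, on the side of fewer depressive symptoms.

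Neither reading identifies severe depression, and no conversion is given. The rule cannot be transferred as it stands.

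**What does the PROMIS report flag?** Above 50 + 2 × 10 = 70, or worsening by 0.5 × 10 = 5 points. Appendix F is consistent with itself. At baseline there is no earlier score, so only a score above 70 can be flagged.

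**Does any section impose a duty to notify?** Sections 7.5.2 and Appendix F make reports available. The provider progress report in 7.6.7 does not mention PRO scores. The coach route (7.6.5) and the weekly survey (Appendix C) pass on reported symptoms, not questionnaire scores. None requires anyone to act on a depression score.

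**Workload of a PROMIS rule at the existing highlight.** Inputs: 55 women (13.1), three assessments (7.5.2), mean 50 and SD 10 (Appendix F). Assumptions: normally distributed T-scores and complete data.

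- Forms: 55 × 3 = 165.
- P(T > 70) = P(Z > 2.0) = 0.0228, and 165 × 0.0228 = 3.8, about 4 notifications.
- The documents give no depression mean for this population. If it were 55 (an assumption, for range only), P(Z > 1.5) = 0.0668, and 165 × 0.0668 = 11.0.

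These counts are of forms, not women, so a persistently high scorer counts up to three times. Missed assessments and exclusion 6.2.5 would lower them. They measure workload, not harm.

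**Burden of adding the PHQ-8.** 8 items × 3 assessments = 24 items per woman.

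**The case against.** The strongest reply is that the sentence is a remnant. It sits in the background section, directly after a list of another study's instruments, and none of the operational safety text (7.3, 7.6.5, section 10, Appendix C) refers to it. On that view no safety procedure has failed.

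Much of this stands, and it is why the point is minor. It does not remove the point. The sentence is written as a commitment of this trial. If it is a remnant it should be replaced or removed; if it is intended, the instrument is missing. Either way the text needs amending.

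The second reply is that clinicians can already see the scores, and this also largely stands. The highlighted report is available to providers, and 7.6 speaks of "usual medical care from their providers (i.e., oncologists and primary care physicians", so the oncologist is plausibly among them. Weekly symptom inquiry runs from month 3 (section 1, 7.3 and Appendix C; 7.6.5 says months 4-6). That is about when Contrave starts, at week 9, so the inquiry covers essentially the whole drug period. Three limits remain:

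- Access to a report is not notification.
- The symptom route depends on the woman reporting a symptom, and the examples in Appendix C include anxiety but not depression.
- Women may be referred from outside the institution (7.3.1), so the primary oncology provider need not be a sub-investigator with REDCap access.

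A reader might infer that severe depression would go unseen in this trial. The documents do not support that, given the report and symptom routes above. A reader might also take a T-score above 70 as equivalent to PHQ-8 ≥15. Nothing in the documents says so: 70 is a general 2-SD highlight shared by several domains. Whether it would notify fewer or more women than 5.10 intends cannot be settled from the text.

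**Conclusion.** The inconsistency is real and of minor severity. The rule in 5.10 cannot be triggered for any participant, because its score is not collected and cannot be derived from the form that is. The gap is the absence of a duty to notify, not the absence of any channel to a clinician. The primary endpoint, sample size, dosing and analysis are untouched.

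The finding itself rests only on the text. The assumptions listed with the calculation bear only on the workload estimate.

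**What to change.** Either of two changes would do.

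**(a) Move the rule to the form already given.** Replace the sentence in 5.10, and mirror it in 7.5.2, with: *The study team (Protocol Chair or designee) will notify the primary oncology provider promptly after questionnaire completion if the PROMIS Depression T-score exceeds 70 at baseline, 2 months or 6 months.* The value of 70 is a default taken from the existing Appendix F highlight. The clinical team should set a lower cut-off if it judges that 70 misses moderately severe depression. The 5-point worsening can stay as a report highlight, and the coach and weekly-survey routes stay unchanged. Cost: a check on a score already collected and a small number of notifications, about 4 from 165 forms at the Appendix F reference mean and more if the mean is higher or the cut-off lower.

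**(b) Collect the PHQ-8.** Add it to 7.5.2 and Appendix E at the same three assessments and keep the ≥15 rule. No new threshold has to be chosen. Cost: 24 more items per woman, overlapping in content with the PROMIS Depression form.

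Either option needs an amendment approved by the IRB (12.2).

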5.11 Summary

Treatment of obesity with pharmacotherapy is underutilized in patients whom are unable to achieve weight loss with behavioral interventions. Our results will be used not only to implement a weight loss program for this vulnerable population of breast cancer patients, but also to develop large scale trials assessing breast cancer-related outcomes. Furthermore, we will identify how pharmacotherapy and behavioral weight loss interventions affect biomarkers of obesity and the microbiome, laying groundwork to future trials investigating additional or alternate interventions in those who are not expected to benefit from the program.

